5.2 Cord Blood Arm

5.2.1 hUCB Collection, Processing and Storage

We will only recruit pediatric subjects who have their hUCB stored with Cord Blood Registry® (CBR) (CBR Systems, Inc., San Bruno, CA) and meet the study entry criteria. CBR is a private cord blood bank accredited by the American Association of Blood Banks (AABB) with an inventory of over 400,000 banked hUCB samples. Their stringent laboratory processes, record keeping and quality control are designed to meet all federal (FDA) and state guidelines and regulations. CBR is licensed by the states of New York, Maryland, New Jersey, California, and Illinois who have their own set of strict regulations for stem cell banks. The CBR laboratory is also CLIA certified.

5.2.2 CBR hUCB Sample Quality

CBR collection methods are virtually free of microbial and fungal contamination as 98% of units are sterile upon testing (Harris, 2008) CBR has extensive experience with Ficoll-Hypaque and AXP processing and is able to attain high stem cell recovery rates as assessed by MNC and TNC recovery rates following processing. Ficoll-Hypaque processing recovers 98% of the MNC fraction (Harris, 2002), while AXP processing recovers 98.7% of the MNC fraction and 96.2% of the TNC fraction (Rosenthal, 2008). CBR has provided 86 hUCB samples for use in transplant to 26 different transplant centers with an average post-thaw viability of >90% based on measures conducted at the transplant centers and all hUCB units released have tested viable (Harris, 2008).

5.2.3 Subject Recruitment

Fifteen pediatric subjects who have their umbilical cord blood banked with CBR and meet study criteria will be enrolled into the cord blood study arm. The parent(s)/LAR of potential subjects will contact CBR. After receiving permission to release the subject's contact information, CBR will then relay the contact information to the research team, who will then contact the parent(s). During this telephone call, an overview of the study and basic eligibility requirements will be reviewed. If eligibility requirements are met and the parent(s)/LAR willing to participate, instructions will be provided on forwarding medical records to the research team for review and a consent and authorization for release of information (for contact with the subjects primary care provider [PCP]) will be sent to the parent(s)/LAR. After receipt of medical records and contact with the PCP (if

indicated) a telephone conference call will be scheduled with the parent(s)/LAR. During the call, study procedures and the informed consent document will be reviewed. Time will be given to answer questions. The parent(s)/LAR will not be pressured to make a decision on participation during the call. Families choosing to participate in the study will be asked to return the signed informed consent in the postage paid envelope provided.

After receipt of the signed informed consent document, CBR will be notified to release cord blood information to the research team. The parent(s)/LAR will be contacted by the research team to schedule the baseline/treatment visit. The parent(s)/LAR will be responsible for making their travel arrangements.

Approximately 4 – 6 weeks prior to the scheduled procedure date, the subject will have the infectious disease testing for HIV 1 and II, Hepatitis B and C, HTLV 1 and II, Syphilis, CMV, and West Nile Virus. An additional 8 – 10 mL of blood will be collected at this time and shipped overnight to a Cell and Gene Therapy (CAGT) lab in Houston for HLA testing. All lab results will be sent to the research team for review prior to the baseline/treatment visit. If the subject has a positive HIV, Hepatitis B, or C test; they will be excluded from the study.

5.2.4 Maternal Infectious Disease Testing

CBR routinely collects a maternal blood sample at the time of delivery for infectious disease marker (IDM) testing. The maternal IDM results (if available) will be released to the research team along with the cord blood sterility and cell count information after informed consent has been obtained and CBR has obtained permission from the parent(s)(s). The infectious disease tests include: Human Immunodeficiency Virus (HIV) type 1, HIV type 2, Hepatitis B virus, Hepatitis C virus, Human T-cell lymphotrophic virus (HTLV) type I, HTLV type II, and Syphilis. If any maternal infectious disease markers were positive at the time of the collection the cord blood will not be used, and the subject will not be eligible, (refer to Appendix D). Per CBR, less than 10% of cord blood collections do not have the maternal IDM testing performed. In the event that a subject meets criteria for study entry, but CBR does not have the maternal IDM results, the parent(s) can submit IDM results that were performed during the pregnancy, for instance as part of the prenatal labs or performed during the hospital admission for delivery. If the IDM tests were not completed during the pregnancy, the mother will be required to have IDM testing completed at her expense and lab results submitted to the PI. If any of the results of the maternal IDM tests are positive, the subject will be ineligible. There is a chance the mother may not have been positive during the pregnancy and the time of delivery; however, we have chosen to err on the side of caution. It is also important to note, that maternal testing is not required under federal regulations for autologous cord blood infusions (CFR 21.1271.90); however, we have chosen to require maternal infectious disease testing in this protocol.

5.2.5 Randomization

Subjects in the hUCB group will be randomized after receipt of subject and maternal infectious disease results and CBR cord blood information on viability and cell count.

Subjects found ineligible for cord blood infusion due to low or non-viable cell count or contamination will be offered the opportunity to enroll in the other treatment arm of the study if the enrollment limit for the BMMNC group has not already been met. The randomization sequence will be computer-generated. The subject will be assigned to the treatment or control arm in a 2:1 ratio using sequentially numbered, opaque, sealed envelopes prepared by a member of the Center for Surgical Trials and Evidence-based Practice (C-STEP) not involved in the clinical trial.

5.2.6 Shipping of Cord Blood

For subjects randomized to receive hUCB at the baseline visit, the GSCL will request a segment of the subject's banked cord blood sample from CBR. The subject's HLA lab results will be compared to the cord blood sample for HLA type (6/6 match). Additionally, the cord blood segment will be tested for viability and cell count. Results from the HLA typing will be faxed to CBR to confirm the subject's identity. CBR will ship the frozen cord blood to the GSCL 7 – 14 days prior to the scheduled procedure, where it will be kept frozen until the morning of infusion. It is important to note that once cord blood has been shipped from CBR it cannot be returned. If the subject is randomized to the placebo group, cord blood unit will NOT be shipped. All HLA lab results will remain on record for reference at the 1 year cross-over visit (if indicated).

5.2.7 Baseline Visit and Cord Blood (Placebo) Infusion

The outpatient baseline visit will be conducted in the Pediatric Outpatient Surgery Clinic. At the baseline outpatient visit, the signed informed consent document will be reviewed with the parent(s)/LAR and assent obtained from the subjects if they are able to do so. During this 1 day outpatient visit, subjects will undergo baseline assessments including physical and neurological exams, laboratory tests, chest radiograph, oxygen saturation monitoring, psychological testing, and quality of life measurements. The neuroexam will be videotaped for blinded assessments of dystonia using standardized scales validated for use on children with CP. The research team will review information from the baseline assessments to ensure the subject remains eligible for participation and that there are no unanticipated reasons to exclude the subject, (such as recent infection). After completing the outpatient baseline visit assessments, eligible subjects will be admitted to a Children's Memorial Hermann Hospital pediatric unit.

The baseline DTMRI will be performed as soon as possible following early AM admission with the cord blood/placebo infusion immediately before or after the DTMRI. For subjects receiving cord blood, the GSCL will thaw, process, and transport the cord blood prior to infusion. For subjects randomized to the placebo group, the GSCL will prepare a placebo infusion according to the procedure described previously for the bone marrow placebo arm, with the exception that it will be loaded in a sterile transfer pack identical to the one used for hUCB cellular product, and the infusion medium will be Dextran 40 containing 5% volume/volume human serum albumin. The pack will be labeled in the manner described in the standard operating procedure (identically to the labeling used for the cellular product). The placebo will be transported to the site of administration in the same manner as the cellular therapy product. The infusion rate will be approximately 5cc/minute for both groups.

IRB NUMBER: HSC-MS-12-0876
UTHealth IRB APPROVAL DATE: 10/23/2017

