1.1 Primary Objective

To determine if autologous cells using either BMMNCs or hUCBs are safe to administer in children with CP.

Primary safety outcome measures:

- 1. In-hospital infusion toxicity: pulmonary and hepatic function; new seizures, hemorrhagic lesions or ischemic lesions on imaging.
- 2. Long-term safety: development of new mass lesions or other pathological structural changes; worsening neurological status.

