5.1.3 Baseline Visit and Bone Marrow (Placebo) Harvest/Infusion

The outpatient baseline visit will be conducted in the Pediatric Outpatient Surgery Clinic. At the baseline outpatient visit, the signed informed consent document will be reviewed with the parent(s)/LAR and assent obtained from the subjects if they are able to do so. During this 1 day outpatient visit, subjects will undergo baseline assessments including physical and neurological exams, laboratory tests, chest radiograph, oxygen saturation monitoring, psychological testing, and quality of life measurements. The neuroexam will be videotaped for blinded assessments of dystonia using standardized scales validated for use on children with CP. The research team will review information from the baseline assessments to ensure the subject remains eligible for participation and that there are no unanticipated reasons to exclude the subject, (such as recent infection). After completing the outpatient baseline visit assessments, eligible subjects will be admitted to a Children's Memorial Hermann Hospital pediatric unit.

The bone marrow harvest will be performed under sedation (Propofol) and local anesthetic before or immediately after the baseline DTMRI. The subject may be logrolled to a 45 degree angle for access to the posterior iliac crest or remain supine to access anterior iliac crest. The bone marrow harvest will be performed under aseptic conditions. The bone marrow harvest is performed using either an 11-gauge needle or 15-gauge needle inserted into the iliac crest(s). Approximately 2 – 3 mL (< 40 kg body weight) to 5 – 6 mL (> 40 kg body weight) of bone marrow aspirate will be obtained and transferred in as sterile manner in a validated Coleman® cooler at ambient temperature to the Griffin Stem Cell Laboratory (GSCL). An additional blood sample will be drawn for infectious disease testing that includes HIV 1 and II, Hepatitis B and C, HTLV 1 and II, Syphilis, CMV, West Nile Virus, and ABO blood type. Transportation, processing, assessing and quality assurance at GSCL are described in the Chemistry & Manufacturing section of the IND. Approximately 6 – 7 hours after bone marrow aspiration, subjects will receive the BMMNC via peripheral or central intravenous infusion in a time not to exceed 30 minutes. The product will be infused within 30 minutes of receipt at Children's Memorial Hermann Hospital, and will remain in the cooler until ready for infusion.

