5.2.8 Schedule of Vital Signs during and Post-Infusion

- 1. Immediately prior to infusion
- 2. During infusion: vital signs continually monitored & recorded every 5 minutes
- 3. Post Infusion: q 15 minutes x 4 (1st hour), q 30 minutes x 4 (next 2 hours), q 1 hour x 4 (next 4 hours), and then every 4 hours thereafter.

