5.2.10 Cross-Over and Follow-Up Visits

As part of the trial, the subjects will return to The University of Texas Health Science Center at Houston for 3 follow-up visits: 6 months (+/- 14 days), 1 year post-treatment (+/- 21 days), and 2 years post-treatment (+/- 21 days). Each visit will take place over 1-2 days, and the subject will undergo outpatient assessments which include physical and videotaped neurological exams, laboratory tests, chest radiograph, oxygen

saturation monitoring, psychological testing, and quality of life measures. DTMRI will be performed at the 1 and 2 year post-treatment visits.

Prior to scheduling the 1 year follow-up visit, the treatment blind will be broken and the parent(s) notified. At this time, the parent(s) of children in the placebo group may choose to have their child admitted to the Children's Memorial Hermann Hospital Pediatric ICU/MICU for cord blood cell infusion. If the subject's parent(s) agrees to the cord blood infusion, the study coordinator will notify the Director of GSCL of the scheduled visit date. The Director will then request that the cord blood be shipped from CBR. The frozen cord blood unit will be shipped overnight to the GSCL 7 – 14 days prior to the scheduled procedure. The cord blood will be kept frozen until the morning of the infusion. All procedures will be followed in the same manner as was done for the Treatment Group.

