6.4.9 Secondary Imaging Outcome Measures & Correlation with Functional Outcome

As noted in the section, "CP Neuroimaging", cerebral palsy is a clinical diagnosis comprising a heterogeneous group of patients. This heterogeneity is manifest both in the dominant clinical symptom complex, but also in the imaging correlates of the symptoms. To that end, prior to treatment this study will quantify the degree of functional impairment (GFCMS level), and correlate it with the CP subtype and imaging abnormality. The imaging ROIs will be prospectively identified pre-treatment. Then, according to the qualitative and quantitative metrics, the imaging data will be recorded. Post-treatment, these same ROIs will be compared to the baseline data, and correlated with any changes in functional outcomes as measured by specific tasks on the GFCMS. Ultimately, the changes in WM and GM ROIs that are associated with CP will be compared with and without treatment using autologous bone marrow derived mononuclear cells or autologous cord blood mononuclear cells. These data will provide a structural metric around which future studies could be powered. Further, these data may provide potential mechanistic targets in terms of structural preservation and restoration in patients with CP.

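### Cord-blood arm: the baseline MRI may follow the infusion; in both arms, in-hospital imaging lesions have no scheduled before-and-after scan

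*Combined protocol and SAP*

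**What the plan says.** **Order of scan and infusion.** Section 5.2.7 places the cord-arm baseline scan on the morning of admission, "with the cord blood/placebo infusion immediately before or after the DTMRI". Section 5.2.10 then says of the crossover admission: "All procedures will be followed in the same manner as was done for the Treatment Group". In the bone-marrow arm the choice of order concerns the harvest, not the infusion. Section 5.1.3 puts the harvest under sedation and "local anesthetic before or immediately after the baseline DTMRI", with the infusion about 6 to 7 hours after the harvest.

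**Use of the baseline scan.** Section 6.4.9 states "The imaging ROIs will be prospectively identified pre-treatment" and that after treatment "these same ROIs will be compared to the baseline data". Section 1.2 also ties identification of the white matter tracts to the baseline MRI. Section 9.1.2 analyses volumes, FA and MD at baseline, 1 year and 2 years.

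**Safety outcomes that need imaging.** Section 1.1 lists, as outcome 1, "In-hospital infusion toxicity: pulmonary and hepatic function; new seizures, hemorrhagic lesions or ischemic lesions on imaging" and, within outcome 2 (long-term), "development of new mass lesions or other pathological structural changes".

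**Scheduled scans.** In both arms Appendix A marks DT-MRI at the first admission, the 1-year follow-up visit, the crossover admission and the 2-year visit. It marks none at the 1-year crossover clinic visit, on Post-Infusion Day 1 or on Days 2 to 21.

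**The concern.** A baseline taken after the infusion is not a pre-treatment measurement. Any early infusion-related change would be absorbed into the reference value, and a lesion arising then would look pre-existing at 1 year. By that time the cord-arm scan may also follow the premedication (section 5.4) and, with the cellular product, the extra saline (section 6.2.1). The bone-marrow scan is in practice taken before all of this, so the two arms' baselines may differ in kind. At crossover the same freedom could put a control child's 1-year scan after the first cell dose, inside what is meant to be the sham period.

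The second gap is independent of order. With one scan per admission, the in-hospital hemorrhagic or ischemic lesion item has no scheduled means of ascertainment. A report of no such lesions could be read as if every child had been screened.

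**Working it through.** The plan states no figure on this point, so there is none to reproduce. The check sets the sections side by side and counts scans.

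**1. Do the sections conflict?** If the scan precedes the infusion, 5.2.7 and 6.4.9 agree. If the infusion comes first, as 5.2.7 permits, the baseline scan is post-treatment and 6.4.9 fails. Appendix A puts scan and infusion in one admission column without an order, so it does not settle the matter.

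**2. Can the order be recovered?** Section 5.2.8 requires "During infusion: vital signs continually monitored & recorded every 5 minutes", so the infusion time is on record. No section asks for the scan order to be recorded or used in the analysis.

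**3. How many scans are exposed?** Inputs are 30 children, 15 per arm, randomized 2:1 (section 3).
- Per arm: 10 treated + 5 sham. Trial: 20 treated + 10 sham.
- Cord-arm baselines: 10 + 5 = 15 of 30, so the range is 0 to 15.
- Changes from baseline (1 and 2 years): 15 × 2 = 30 of 30 × 2 = 60, so 0 to 30.
- Control 1-year scans: Appendix A gives the crossover clinic visit no MRI but gives the crossover admission one. The natural reading is that the admission scan serves as that child's 1-year scan, so 0 to 5 of 10. The text does not say this outright.

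**4. What would setting the scans aside cost?** This is a scenario: a simple two-group comparison of change, both arms pooled, complete data, in SD units. It fits the 1-year contrast; by 2 years control children may have crossed over.
- SE = √(1/n₁ + 1/n₂).
- None set aside: √(1/20 + 1/10) = 0.387. 95% half-width 2.048 × 0.387 = 0.79 SD (28 df).
- All 15 set aside: √(1/10 + 1/5) = 0.548. 95% half-width 2.160 × 0.548 = 1.18 SD (13 df).
- Ratio of SEs: 0.548 / 0.387 = 1.41, a rise of 41%.

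**5. In-hospital before-and-after pairs.** A pair needs two scans in one admission, and each admission has one. Scheduled pairs are therefore 0 of 30 initial infusions and 0 of up to 10 crossover infusions. Changing the order does not alter this.

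**6. Do other provisions close the gap?** Hourly neurologic checks (section 6.2.5) cover symptomatic events, and the stopping rules (section 10.8.1) do not use routine scans. Sections 10.6.2.1 and 10.7 allow an abnormality judged temporally related to be recorded as an adverse experience. At the first admission that is weak support: a normal brain MRI is an exclusion (section 4.2), so these children already have abnormal scans, and without a pre-infusion study scan a lesion cannot reliably be called new.

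**The case against.** **Scan-first is probably the usual order.** Section 5.2.7 asks for the scan as soon as possible after an early-morning admission. The cord unit is still frozen that morning (5.2.6) and must be thawed, processed, washed and transported, with premedication 30 minutes before infusion (5.4). This stands as a reason to expect a count nearer 0 than 15. It is not a rule, and the text expressly permits the other order.

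**An earlier MRI may exist.** Excluding children with a normal MRI implies either a prior clinical scan or a baseline scan read before infusion. This stands in part. A prior scan could help date a lesion, but its date and sequences are unspecified and it cannot replace a volumetric and DTI baseline. Section 6.4.1 also lists regions from the literature, so some region selection does not depend on scan order; the baseline values still do.

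**The crossover reading is inferred.** Section 5.2.10 places the MRI at the 1-year visit for all subjects. This stands, and the 0-to-5 range is conditional on the reading of Appendix A.

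**The precision loss is hypothetical.** Nothing in the documents shows that volume, FA or MD shifts immediately after infusion. This stands. The 1.18 SD figure is the price of discarding every cord-arm baseline, not an estimate of bias.

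**Scanning first gives something up.** A post-infusion cord-arm scan is the only scheduled in-hospital brain imaging that could show an acute lesion. True, but without a prior study scan it could not show the lesion to be new, so little is lost.

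**Conclusion.** The concern holds, and both parts should be fixed.

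**Cord-arm order.** Sections 5.2.7 and 5.2.10 contradict 6.4.9 (and sit badly with 1.2) whenever the infusion comes first. Exposure is 0 to 15 of 30 baselines, 0 to 30 of 60 changes and, on the natural reading of Appendix A, 0 to 5 of 10 control 1-year scans. The upper limit of 15 assumes that bone-marrow scans precede infusion, which the harvest timing implies but the text does not state. The number actually affected, and the size and direction of any bias, are unknown. The effect is confined to the secondary imaging comparisons and the long-term structural safety outcome.

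**In-hospital lesion item.** With 0 scheduled pairs in either arm, this item has no stated method of ascertainment. It is the smaller point, since a clarifying line would repair it.

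**What to change.** **Order.** Reconcile 5.2.7, 5.2.10 and 6.4.9. State that the study DTMRI precedes the cell or placebo infusion at both the initial and the crossover admission, an order that 5.2.7 already allows, and record both times on the CRF. For children already treated, establish the order from the infusion vital-sign record and the scan time. Report how many were scanned after infusion, and repeat the imaging analysis without those scans as baseline (or as 1-year control scans for crossover children).

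**In-hospital lesions.** Keep the item in outcome 1 and add one line to 1.1: in-hospital hemorrhagic or ischemic lesions are ascertained only through clinically prompted imaging, reported as number imaged and number with a new lesion. Judge silent lesions under outcome 2: at 1 year against the pre-infusion scan or, for crossover children, at 2 years against the pre-infusion crossover-admission scan. The sponsor could instead schedule a second in-hospital scan, but at the cost of added imaging.

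**Cost.** The proposed changes add no scan but need IRB approval as a protocol modification (section 11.1). They reduce scheduling flexibility on the infusion day, including around the morning thaw. Section 6.4.2 puts the imaging at about 20 minutes; the times listed in Figure 4 sum to 30 + 165 + 165 + 72 + 311 + 172 = 915 s, or 15 min 15 s. Re-acquisition for motion takes longer. Silent in-hospital lesions would remain unscreened, and the trial would say so.
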